## **APPENDIX 4. ACTIONS REQUIRED IN CASES OF INCREASES IN LIVER BIOCHEMISTRY AND EVALUATION OF HY'S LAW**

### **Introduction**

This Appendix describes the process to be followed to identify and appropriately report cases of Hy's Law. It is not intended to be a comprehensive guide to the management of elevated liver biochemistries.

During the study the investigator will remain vigilant for increases in liver biochemistry. The investigator is responsible for determining whether a subject meets potential Hy's Law (PHL) criteria at any point during the study.

The investigator participates, together with Viela Bio clinical project representatives, in review and assessment of cases meeting PHL criteria to agree whether Hy's Law (HL) criteria are met. HL criteria are met if there is no alternative explanation for the elevations in liver biochemistry other than Drug Induced Liver Injury (DILI) caused by the investigational product.

The investigator is responsible for recording data pertaining to PHL/HL cases and for reporting adverse events (AE) and serious adverse events (SAE) according to the outcome of the review and assessment in line with standard safety reporting processes.

### **Definitions**

#### **Potential Hy's Law (PHL)**

Aspartate aminotransferase (AST) or alanine aminotransferase (ALT)  $\geq 3 \times$  upper limit of normal (ULN) together with total bilirubin (TBL)  $\geq 2 \times$  ULN at any point during the study following the start of investigational product irrespective of an increase in alkaline phosphatase (ALP).

#### **Hy's Law (HL)**

AST or ALT  $\geq 3 \times$  ULN together with TBL  $\geq 2 \times$  ULN, where no other reason, other than the investigational product, can be found to explain the combination of increases; e.g., elevated ALP indicating cholestasis, viral hepatitis, another drug.

For PHL and HL the elevation in transaminases must precede or be coincident with (i.e., on the same day) the elevation in TBL, but there is no specified timeframe within which the elevations in transaminases and TBL must occur.

#### **Identification of Potential Hy's Law Cases**

To identify cases of PHL it is important to perform a comprehensive review of laboratory data for any subject who meets any of the following identification criteria in isolation or in combination:

- ALT  $\geq 3 \times$  ULN
- AST  $\geq 3 \times$  ULN
- TBL  $\geq 2 \times$  ULN

The investigator will without delay review each new laboratory report and if the identification criteria are met will:

- Notify the sponsor study representative
- Determine whether the subject meets PHL criteria by reviewing laboratory reports from all previous visits
- Promptly enter the laboratory data into the laboratory eCRF

## **Follow-up**

### **Potential Hy's Law Criteria Are Not Met**

If the subject does not meet PHL criteria the investigator will:

- Inform the sponsor representative that the subject has not met PHL criteria
- Perform follow-up on subsequent laboratory results according to the guidance provided in the Clinical Study Protocol.

### **Potential Hy's Law Criteria Are Met**

If the subject does meet PHL criteria the investigator will notify the sponsor study representative who will then inform the central study team. The medical monitor contacts the investigator, to provide guidance, discuss and agree an approach for the study subjects' follow-up and the continuous review of data. After this contact the investigator will:

- Monitor the subject until liver biochemistry parameters and appropriate clinical symptoms and signs return to normal or baseline levels, or as long as medically indicated
- Investigate the etiology of the event and perform diagnostic investigations as discussed with the medical monitor.
- If at any time (in consultation with the medical monitor) the PHL case meets serious criteria, report it as an SAE using standard reporting procedures

## **Review and Assessment of Potential Hy's Law Cases**

The instructions in this section should be followed for all cases where PHL criteria are met.

No later than 3 weeks after the biochemistry abnormality was initially detected, the medical monitor will contact the investigator to review available data and agree on whether there is an alternative explanation for meeting PHL criteria other than DILI caused by the investigational product. The medical monitor and safety physician will also be involved in this review together with other subject matter experts as appropriate.

According to the outcome of the review and assessment, the investigator will follow the instructions below.

If there is an agreed alternative explanation for the ALT or AST and TBL elevations, a determination of whether the alternative explanation is an AE will be made and subsequently whether the AE meets the criteria for a SAE:

- If the alternative explanation is not an AE, record the alternative explanation on the appropriate eCRF
- If the alternative explanation is an AE/SAE, record the AE /SAE in the eCRF accordingly and follow the sponsor standard processes

If it is agreed that there is no explanation that would explain the ALT or AST and TBL elevations other than the investigational product:

- Report an SAE (report term ‘Hy’s Law’) according to sponsor standard processes.
- The ‘Medically Important’ serious criterion should be used if no other serious criteria apply
- As there is no alternative explanation for the HL case, a causality assessment of ‘related’ should be assigned.

If, there is an unavoidable delay, of over 3 weeks, in obtaining the information necessary to assess whether or not the case meets the criteria for HL, then it is assumed that there is no alternative explanation until an informed decision can be made:

- Report an SAE (report term ‘Potential Hy’s Law’) applying serious criteria and causality assessment as per above
- Continue follow-up and review according to agreed plan. Once the necessary supplementary information is obtained, repeat the review and assessment to determine whether HL criteria are met. Update the SAE report according to the outcome of the review

FDA Guidance for Industry (issued July 2009) ‘Drug-induced liver injury: Premarketing clinical evaluation’:

<http://www.fda.gov/downloads/Drugs/GuidanceComplianceRegulatoryInformation/Guidances/UCM174090.pdf>

Signature Page for VV-CLIN-001574 v4.0

| BPAR | biopsy-proven acute rejection |
| CMV | cytomegalovirus |
| CSR | clinical study report |
| CTCAE | common terminology criteria for adverse events |
| DGF | delayed graft function |
| CCI | [REDACTED] |
| HLA | human leukocyte antigen |
| IP | investigational product |
| IV | intravenous |
| PK | pharmacokinetics |
| PRA | Panel Reactive Antibody test |
| PT | preferred term |
| QTc | corrected QT interval |
| SAE | serious adverse event |
| SOC | system organ class |
| SPP | statistical programming plan |
| tBPAR | treated biopsy-proven acute rejection |
| TEAE | treatment-emergent adverse event |
| TESAE | treatment-emergent serious adverse event |

1 INTRODUCTION

This document describes the statistical analysis for protocol VIB4920.P2.S1, a Phase 2a, prospective single-arm, open-label pilot study to evaluate the efficacy, safety, and tolerability of dual costimulation blockade with VIB4920 + belatacept in adult male or female recipients of a renal allograft from a deceased, living unrelated, or human leukocyte antigen (HLA) non-identical living related donor.

2 STUDY OVERVIEW

2.1 Study Objectives and Endpoints

The objectives and corresponding endpoints are listed in [Table 1](#) below:

Table 1 Study Objectives and Endpoints

| Primary objective | Endpoints/variables |
|---|--|
| 
 To demonstrate that, when added to standard-of-care induction regimen that includes Thymoglobulin® (anti-thymocyte globulin [rabbit]) and corticosteroids, dual costimulation blockade with multiple doses of VIB4920 + belatacept, started at the time of kidney transplant surgery and repeated every 2-4 weeks post-transplantation, prevents composite efficacy failure (tBPAR of grade 1A or higher, graft loss, or death) at Week 24 post-transplantation in the majority of subjects ($\geq 17/20$) | 
 Incidence of efficacy failure, defined as treated biopsy-proven acute rejection (tBPAR) of grade 1A or higher, graft loss, or death, at Week 24 post-transplantation |
| Secondary objectives | Endpoints/variables |
| 
 To evaluate individual components (and combinations of the individual components) of the composite efficacy endpoint at Weeks 12, 24, and 48 post-transplantation. | 
 Incidence of efficacy failure, defined as treated biopsy-proven acute rejection (tBPAR) of grade 1A or higher, graft loss, or death, at Weeks 12 and 48 post-transplantation Incidence of tBPAR, graft loss, death, or loss to follow-up at Weeks 12, 24, and 48 post-transplantation Incidence of antibody-mediated rejection at Weeks 12, 24, and 48 post-transplantation Incidence of tBPAR at Weeks 12, 24, and 48 post-transplantation Incidence of BPAR at Weeks 12, 24, and 48 post-transplantation Incidence of treated acute rejections at Weeks 12, 24, and 48 post-transplantation Proportion of subjects with de novo donor-specific antibodies (dnDSA) at Weeks 12, 24, and 48 post-transplantation |
| 
 To evaluate safety and tolerability of dual costimulation blockade with VIB4920 + | 
 Treatment-emergent adverse events and treatment-emergent serious adverse events (TEAE and TESAE) |

Table 1 Study Objectives and Endpoints

| | |
|---|---|
| belatacept in subjects receiving a kidney transplant | 
 • Treatment-emergent adverse events of special interest (TEAESI) • Laboratory data by visit • Vital signs data by visit • ECG data by visit |
| 
 • To evaluate the pharmacokinetics (PK) and immunogenicity (anti-drug antibodies [ADA]) of VIB4920 | 
 • VIB4920 plasma concentration over visits • PK parameters • Proportion of subjects who develop detectable ADA |
| Exploratory objectives | Endpoints/variables |
| 
 • Evaluate CCI [redacted] at Weeks 4, 12, 24, and CCI [redacted] in subjects receiving a kidney transplant | 
 • Proportion of subjects with CCI [redacted] at Weeks 12, 24, and 48 • Changes in CCI [redacted] between Week 4 and Week 24; Week 4 and Week 48; and Week 24 and Week 48 |
| 
 • To understand CCI [redacted] in CCI [redacted] and CCI [redacted] in blood related to pharmacology of VIB4920 | 
 • Changes over time in CCI [redacted] related to VIB4920 pharmacology |
| 
 • To evaluate the CCI [redacted] of CCI [redacted] on CCI [redacted] | 
 • Changes over time in the CCI [redacted] and CCI [redacted] |

ADA = anti-drug antibodies; dnDSA = de novo donor-specific antibodies; ECG = electrocardiogram; CCI [redacted] MDRD = modification of diet in renal disease; PK = pharmacokinetics; tBPAR = treated biopsy-proven acute rejection; TEAE = treatment-emergent adverse event; TEAESI = treatment-emergent adverse event of special interest; TESAE = treatment-emergent serious adverse event

2.2 Study Design

2.2.1 Overview

This is a single-arm, open-label exploratory study. The study will be conducted at 2 centers in the United States in a total of approximately 20 subjects. All eligible subjects will undergo the scheduled kidney transplant on Day 0 and be treated with VIB4920 + belatacept (with Thymoglobulin and corticosteroids) according to the following regimen:

[figure not shown]
- Thymoglobulin 1.5 mg/kg by intravenous (IV) infusion prior to reperfusion of the allograft on the day of transplantation surgery (Day 0), prior to VIB4920+belatacept infusion on post-op Day 1, on post-op Day 2, and prior to VIB4920+belatacept infusion on post-op Day 3 or 4
- Methylprednisolone by IV infusion (500, 250, 125 and 60 mg on Days 0, 1, 2 and 3, respectively) followed by oral administration of prednisone 30 mg per day on Days 4, 5, 6 and 7. Subjects may be tapered to at least 20 mg per day on Day 8, to at least 10 mg per

day on Day 15, and to at least 5 mg per day on Day 22. Discontinuation of prednisone should occur following the post-op Day 28 visit.

- VIB4920 1500 mg by IV infusion on post-op Days 1, repeated on post-op Day 3 or 4 (timing is at investigator’s discretion), Week 2, and at the end of Weeks 4, 6, 8, and 10; then 1500 mg every 4 weeks from Week 12 to Week 48.
- Belatacept 10 mg/kg by IV infusion on post-op Day 1 (first dose \geq 12 hours after Thymoglobulin infusion ends), repeated on post-op Day 3 or 4 (timing is at investigator’s discretion), and at the end of Weeks 2, 4, 8, and 12; then 5 mg/kg IV every 4 weeks from Week 16 to Week 48.

VIB4920 should be administered prior to belatacept. The basic study flow diagram is presented in [Figure 1](#).

Figure 1 Study Flow Diagram

2.3 Sample Size

The protocol was amended after 3 subjects were enrolled under the protocol v2.0. Approximately 20 subjects will be enrolled under protocol v3.0.

Belatacept added to standard induction therapy (basiliximab, mycophenolate mofetil, corticosteroids) resulted in efficacy failure in 21.7% of recipients of living- and standard criteria deceased-donor kidneys by 1 year (Nulojix[®] USPI). With 20 subjects, if 3 or fewer subjects are observed with efficacy failure (ie, response rate \geq 85%) at week 24, there is $>$ 89% confidence that the response rate is at least 70%.

3 STATISTICAL METHODS

3.1 General Considerations

All statistical calculations will be primarily performed using SAS[®] System Version 9.4 or higher. Categorical data will be summarized by the frequency counts and percentage of subjects in each category. Continuous variables will be summarized by descriptive statistics, including number of observations, mean, standard deviation, median, first quartile, third quartile, minimum, and maximum.

3.1.1 Definition of Baseline

In general, baseline will be defined as the last non-missing valid observation prior to the first administration of VIB4920 or belatacept, whichever occurs first. In cases where baseline measurements are taken on the same day as investigational product (IP) and no times are reported, it will be assumed that these measurements are taken prior to IP being administered.

For **CCI** the baseline will be defined as Week 4 measurement.

3.1.2 Analysis Windows

Analysis visit windows will be used for all visit-based assessments to map longitudinal observations to scheduled visits and, thereby, allow for by-visit analyses, since not all assessments are performed on the scheduled day. Unless otherwise specified, all longitudinal efficacy and safety data analyses will be based on the analysis visit windows. The analysis visit windows will be calculated by bisecting the interval between adjacent scheduled visit days and will be specified in the statistical programming plan (SPP).

The actual assessment day will be mapped to the windows defined for each scheduled study visit with following rules:

- If more than one assessment falls within a visit window, the closest non-missing assessment to the scheduled day will be used in the analysis.
- If 2 non-missing assessment actual dates are equidistant from the target day, the later visit will be used in the analysis.
- For retest values of laboratory data, the retest value (the last valid observation assessed on the same visit day) will be chosen.

3.2 Protocol Deviations

All protocol deviations will be classified as either major protocol deviations or minor protocol deviations. The major protocol deviations are considered as the important protocol deviations, which may significantly impact the completeness, accuracy, and/or reliability of the study data, and may significantly affect a subject's rights, safety, or well-being. All the protocol deviations will be listed, and the major protocol deviation will be summarized. Some classifications of major protocol deviations are listed below.

- Did not meet inclusion criteria or met exclusion criteria.
- Received prohibited concomitant medication.
- Met IP discontinuation criteria but was not discontinued from the IP.
- Serious breach of good clinical practice.

The list may be updated and will be finalized and documented prior to the database lock.

3.3 Analysis Sets

3.3.1 Safety analysis set

The safety analysis set includes all subjects who received any dose of IP. The safety, pharmacodynamics, and anti-drug antibodies (ADA) analyses will be based on the safety analysis set.

3.3.2 Efficacy evaluable set

Efficacy evaluable set includes all subjects who received the revised regimen of Thymoglobulin and steroids, and any dose of IP. The efficacy analysis will be based on the efficacy evaluable set.

3.3.3 Pharmacokinetics analysis set

[figure not shown]
The pharmacokinetics (PK) analysis set includes all subjects who receive IP and have at least one quantifiable serum PK observation post-first dose. PK analyses will be based on the PK analysis set.

3.4 Study Subjects

3.4.1 Subject Disposition

A summary of subject disposition will be presented using the categories presented in [Figure 2](#).

Figure 2 Subject Disposition

3.4.2 Demographics, Baseline Characteristics, and Medical History

The demographics (age, gender, race, ethnicity, height, weight, and body mass index) will be summarized.

Subject background information, including end-stage renal disease leading to transplantation, current dialysis (none, hemodialysis, peritoneal dialysis), highest Panel Reactive Antibody (PRA) test, most recent PRA, and HLA type, will be summarized. Donor background information, including sex, race, ethnicity, transplant donor type (living related, living unrelated, deceased heart beating, deceased non-heart beating), will be summarized as well.

Significant medical history finding will be summarized by MedDRA system organ class (SOC) and preferred term (PT).

3.4.3 Study Drug Exposure

VIB4920 and belatacept

The number of doses received, amount of the study drug received, durations of the study drug exposure, and treatment compliance will be summarized for VIB4920 and belatacept separately.

- Durations of the study drug exposure = last dose date + 28 – first dose date + 1.
- The amount of study drug exposure: if a subject received partial dose at a dosing visit, then the amount of study drug at that dosing visit will be estimated based on the actual volume administered.
- Treatment compliance for an individual subject = [Total number of doses received]/ [Total number of doses planned per protocol] × 100%.

Thymoglobulin and corticosteroids

Subjects will receive IV thymoglobulin 1.5 mg/kg prior to reperfusion of the allograft on the day of transplantation surgery (Day 0), prior to VIB4920+belatacept infusion on post-op Day 1, on post-op Day 2, and prior to VIB4920+belatacept infusion on post-op Day 3 or 4. Number (%) of subjects who received thymoglobulin will be summarized by Day.

Subjects will receive methylprednisolone by IV infusion (500, 250, 125, and 60 mg on Days 0, 1, 2, and 3, respectively) followed by oral administration of prednisone 30 mg per day on Days 4, 5, 6 and 7. Subjects may be tapered to at least 20 mg per day on Day 8, to at least 10 mg per day on Day 15, and to at least 5 mg per day on Day 22. Discontinuation of prednisone should occur following the post-op Day 28 visit. The methylprednisolone and oral prednisone dose in mg/day will be summarized by Day (Days 0, 1, 2, 3, Day 4 - Day 7, Day 8 - Day 14, Day 15 - Day 21, Day 22 - Day 28). The total corticosteroid dose in mg will also be summarized.

3.4.4 Prior and Concomitant Medications

Number (%) of subjects who received prior medications and concomitant medications will be summarized by WHO Drug dictionary. At each level of summarization, a subject is counted

once if the subject reported one or more medications at that level. The prior and concomitant medications are defined as below.

- Prior medications are defined as medications with a stop date occurring before the IP administration date.
- Concomitant medications are defined as medications with a start date on or after the IP administration date or stop date occurring on or after the IP administration date.

The missing start/stop date will be imputed as appropriate and the details of the imputation will be included in the SPP.

Number (%) of subjects who received the following medications will be summarized.

- Medications used for the treatment of suspected or confirmed acute rejections.
- Prophylaxis medications for each of cytomegalovirus (CMV), Pneumocystis jirovecii pneumonia, and oral Candida.

3.5 Efficacy Analyses

3.5.1 Primary Efficacy Endpoint(s) and Analyses

3.5.1.1 Primary efficacy endpoint

The primary efficacy endpoint is the incidence of efficacy failure, defined as treated biopsy-proven acute rejection (tBPAR) of grade 1A or higher, graft loss, or death at Week 24 post-transplantation.

3.5.1.2 Primary efficacy analysis

For the primary efficacy analysis, the acute rejection rating will be based on the consensus of the pathologists at the 2 participating sites.

The primary efficacy endpoint will be analyzed descriptively. The incidence of efficacy failure, defined as tBPAR of grade 1A or higher, graft loss, or death at Week 24 post-transplantation, and the corresponding 80% 2-sided exact confidence interval will be calculated. Missing data will not be imputed.

3.5.2 Secondary Efficacy Endpoints and Analyses

3.5.2.1 Secondary efficacy endpoints

The secondary efficacy endpoints are as follows:

- Incidence of efficacy failure defined as tBPAR of grade 1A or higher, graft loss, or death at Weeks 12 and 48
- Incidence of tBPAR, graft loss, death, or loss to follow-up at Weeks 12, 24, and 48
- Incidence of antibody-mediated rejection at Weeks 12, 24, and 48

- Incidence of tBPAR at Weeks 12, 24, and 48
- Incidence of BPAR at Weeks 12, 24, and 48
- Incidence of treated acute rejections at Weeks 12, 24, and 48
- Proportion of subjects with de novo donor-specific antibodies at Weeks 12, 24, and 48

3.5.2.2 Secondary efficacy analysis

The secondary efficacy endpoints will be analyzed in the same way as the primary efficacy endpoint.

3.5.3 Exploratory Efficacy Endpoints and Analyses

3.5.3.1 Exploratory efficacy endpoints

The exploratory efficacy endpoints are as follows:

- Proportion of subjects with CCI [REDACTED] at 12, 24, and 48 weeks
- Changes in CCI [REDACTED] between Week 4 and Week 24; Week 4 and Weeks 48; and Week 24 and Week 48

3.5.3.2 Exploratory efficacy analyses

Proportion of subjects with CCI [REDACTED] and the CCI [REDACTED] 2-sided exact confidence interval will be calculated. The CCI [REDACTED] will be summarized by visit. The missing CCI [REDACTED] will not be imputed.

3.6 Safety Analysis

3.6.1 Adverse Events

In general, if an adverse event (AE) onset is on or after the first dose of VIB4920 or belatacept, whichever occurs first, the AE will be considered as a treatment-emergent adverse event (TEAE). Otherwise, the AE will be considered as a non-TEAE.

AEs will be coded using the most recent version of MedDRA. All TEAEs will be summarized overall and by MedDRA SOC and PT, by severity and by relationship to IP. Specific AEs will be counted once for each subject for calculating rates, but all events will be presented in subject listings. In addition, if the same AE occurs multiple times within a particular subject, the highest severity and level of causality will be reported.

An overall summary table will be showing the number and percentage of subjects with at least one event in any of the following categories: TEAE, treatment-emergent serious adverse event (TESAE), TEAE with outcome of death, Grade 3 or higher TEAE, TEAE leading to discontinuation of VIB4920, TEAE leading to discontinuation of belatacept, VIB4920 related TEAE, belatacept related TEAE, VIB4920 related TESAE, and belatacept related TESAE.

The TEAEs, TESAEs, TEAEs resulting in death, Grade 3 or higher TEAEs, TEAE leading to discontinuation of VIB4920, TEAE leading to discontinuation of belatacept, VIB4920 related TEAE, belatacept related TEAE, VIB4920 related TESAЕ, and belatacept related TESAЕ will be summarized by SOC and PT. TESAEs will be summarized by serious adverse event (SAE) criteria as well. In addition, a summary of TEAEs sorted by frequency will be presented by PT. The treatment emergent non-SAE will also be summarized by SOC and PT.

An adverse event of special interest (AESI) is one of scientific and medical interest specific to understanding of the IP. AESIs for this protocol include:

- Thrombotic and embolic events
- Hepatic function abnormality (meeting the definition of Hy’s Law)
- Anaphylaxis and clinically significant (common terminology criteria for adverse events [CTCAE] Grade 3 or higher) hypersensitivity reactions
- Immune complex disease
- Severe infusion-related reactions (CTCAE Grade 3 or higher)
- Malignant neoplasm
- Infections:
 - Clinically significant (CTCAE Grade 3 or higher)
 - Opportunistic infections associated with immunosuppression, including (but not limited to): reactivation of latent viral infection (varicella zoster virus, herpes simplex virus, Epstein-Barr virus, JC virus, CMV, BK polyoma virus), fungal infections, and tuberculosis.

Treatment-emergent adverse events of special interest will be summarized by SOC and PT.

Listings will be provided for all TEAEs and non-treatment emergent AEs.

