### **13.2. Adverse and Serious Adverse Events**

#### **13.2.1. Definition of Adverse Events**

##### **13.2.1.1. Adverse Event (AE)**

An AE is defined as any untoward medical occurrence in a patient or clinical investigation subject administered a pharmaceutical product and which does not necessarily have a causal relationship with this treatment. An AE can therefore be any unfavorable and unintended sign (including an abnormal laboratory finding), symptom, or disease temporally associated with the use of a medicinal product, whether or not considered related to the medicinal product.

An AE includes but is not limited to any clinically significant worsening of a subject's pre-existing condition. An abnormal laboratory finding (including ECG finding) that requires medical intervention by the investigator, or a finding judged by the investigator as medically significant should be reported as an AE. If clinical sequelae are associated with a laboratory

abnormality, the diagnosis or medical condition should be reported (e.g., renal failure, hematuria) not the laboratory abnormality (e.g., elevated creatinine, urine RBC increased).

Abnormal laboratory values that are not, in the investigator's opinion, medically significant and do not require intervention should not be reported as AEs.

All AEs occurring between written informed consent signature and the end of the safety follow-up, whether or not they are related to the study, must be recorded in the eCRF.

Adverse events may be treatment emergent (i.e., occurring after initial receipt of investigational product) or non-treatment emergent. A non-treatment-emergent AE is any new sign or symptom, disease, or other untoward medical event that begins after written informed consent has been obtained but before the subject has received investigational product.

Elective treatment or surgery or preplanned treatment or surgery (that was scheduled prior to the subject being enrolled into the study) for a documented pre-existing condition that did not worsen from baseline is not considered an AE (serious or non-serious). An untoward medical event occurring during the prescheduled elective procedure or routinely scheduled treatment should be recorded as an AE or SAE.

Instances of acute rejection are anticipated on this study and have reporting guidelines referenced in Section [12.2](#). Acute rejection and manifestations of symptoms stemming from acute rejection are not reportable as serious adverse events.

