### **13.5. Recording Adverse Events**

AEs spontaneously reported by the subject and/or in response to an open question from the study personnel or revealed by observation will be recorded during the study at the investigational site. For each AE, the investigator will evaluate and report the onset (date and time), resolution (date and time), severity, causality, action taken, serious outcome (if applicable), and whether or not it caused the subject to discontinue the study. The AE term should be reported in standard medical terminology when possible.

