#### **14.1.2. Procedure for Accounting for Missing Data**

All analyses will be based on actual observed data. Missing values will not be imputed.

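### The SAP's treatment-emergent rule looks only at onset, so an adverse event that begins between surgery and the first study-drug dose and then worsens on treatment is left out of the main safety tables

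*SAP*

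**What the plan says.** SAP 3.6.1 (Adverse Events) sets a two-way split. An event is treatment-emergent "if an adverse event (AE) onset is on or after the first dose of VIB4920 or belatacept, whichever occurs first". The next sentence covers every other event: "Otherwise, the AE will be considered as a non-TEAE". Neither sentence refers to a change in severity or seriousness after dosing.

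Protocol 13.2.1.1 uses the same logic: "Adverse events may be treatment emergent (i.e., occurring after initial receipt of investigational product) or non-treatment emergent". It describes the second class as a new sign, symptom or disease that "begins after written informed consent has been obtained but before the subject has received investigational product".

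On timing, SAP 2.2.1 (Overview) puts surgery, the first Thymoglobulin dose and the first methylprednisolone dose on Day 0. For study drug it gives "VIB4920 1500 mg by IV infusion on post-op Days 1, repeated on post-op Day 3 or 4". Belatacept also starts on Day 1.

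On recording, Protocol 13.5.3 collects adverse events from consent, so Day 0 events are captured. Protocol 13.5 states: "For each AE, the investigator will evaluate and report the onset (date and time), resolution (date and time), severity".

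SAP 3.6.1 builds its overall summary and its system-organ-class and preferred-term tables on treatment-emergent events, including the serious, fatal, Grade 3 or higher, discontinuation, related and special-interest subsets. Non-treatment-emergent events get listings.

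**The concern.** An onset-only rule does little harm when not much happens between consent and first dose. Here every subject has major surgery, graft reperfusion and T-cell depletion in that interval. Complications that start then are plausible. Some may worsen once VIB4920 and belatacept are on board, and those are events that a safety table for an immunosuppressive regimen should show.

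The study has a single arm and about 23 treated subjects, with safety and tolerability as a secondary objective. No comparator arm has the same omission to offset it. If such events are left out, the headline safety percentages for the regimen can only be too low.

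**Working it through.** The plan states no figure on this point, so there is none to reproduce. The check applies the rule to the protocol's own timeline and then works out what one lost subject does to a table.

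**1. The window.** Day 0 carries surgery, reperfusion, Thymoglobulin and methylprednisolone. The second Thymoglobulin dose, on Day 1, is given before the study-drug infusion (SAP 2.2.1; Protocol 9.1). Two of the four scheduled Thymoglobulin doses therefore precede the treatment-emergent clock. Protocol 13.5 collects onset time as well as date, but SAP 3.6.1 does not say whether time is used to split Day 1 events. A Day 0 onset falls before first dose either way.

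**2. The rule applied to an example.** Take an event with onset on Day 0 at Grade 2 that reaches Grade 4 on Day 3 and is kept as one record. First dose is on Day 1.

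- Current rule: treatment-emergent if onset day ≥ first-dose day. 0 ≥ 1 is false, so the event is non-treatment-emergent.
- With a worsening clause: treatment-emergent if onset day ≥ first-dose day, or if the grade after first dose exceeds the grade before it. 4 > 2 is true, so the event is treatment-emergent.

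Under the current rule the event is missing from the TEAE and Grade 3 or higher tables. If it is serious it is also missing from the serious table, and if it is of special interest, from that table too. The SAP 3.6.1 provision on reporting the highest severity concerns the same event occurring several times in a subject. It gives no stated route for bringing a Day 0 record into the treatment-emergent tables.

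**3. Whether another text closes the gap.** Protocol 13.2.1.1 counts clinically significant worsening of a pre-existing condition as an adverse event. Footnote g of Protocol Table 3 has clinically significant changes from the baseline physical examination recorded as adverse events. A site that opened a new record on these grounds, dated at the worsening, would create a treatment-emergent event. Neither text tells sites to do so when an event that began after consent gets worse. Protocol 13.5 asks for onset, resolution and severity for each event and does not mention a change of grade.

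**4. Effect per subject.** The safety set is all subjects who received any investigational product (SAP 3.3.1). SAP 2.3 reports 3 subjects enrolled under protocol v2.0 and about 20 under v3.0:

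- n ≈ 3 + 20 = 23, assuming all were dosed
- One subject lost from a table: 1/23 = 4.3 percentage points

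This applies when the subject has no other event qualifying for the same table. For a single preferred-term row the condition is easier to meet, because only another qualifying event under the same term would keep the subject in the row.

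**5. Direction.** Adding a worsening clause can move events into the treatment-emergent class and cannot move any out. The onset-only count is therefore never higher than the count with the clause.

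**The case against.** The strongest reply is that little is truly hidden.

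- SAP 3.6.2 tabulates toxicity grades, shifts of at least two grades to the worst post-baseline value, and potential Hy's law cases.
- SAP 3.6.3 summarizes delayed graft function, which Protocol 13.1 dates to reperfusion, and counts vital-sign and QTc threshold crossings.
- Death and graft loss are in the primary endpoint.
- Sites may open new records for worsening.
- The recorded Day 0 volume is reduced, since non-serious electrolyte abnormalities within 30 days need not be recorded and rejection is not reported as an adverse event.
- SAP 3.6.1 opens with a general qualifier, and its rule follows the protocol's own definition.

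Much of this stands. A reader might infer that the affected events survive only in a listing, and the summaries above show that this goes too far. They are partial, however. The grade shifts cover only hematology, chemistry and coagulation, and delayed graft function is reported as a proportion without grade or seriousness. A wound, cardiac or infectious event that begins on Day 0 and worsens has no stated equivalent. The general qualifier comes with no stated exception. Agreement between SAP and protocol means that both share the gap. On serious events they do not fully agree: Protocol 14.2.2.2 says SAEs will be summarized without restricting them to treatment-emergent ones, whereas the SAP's serious-event tables are so restricted.

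Two further inferences should be resisted:

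- **Missing onset dates.** Because Protocol 14.1.2 states "All analyses will be based on actual observed data. Missing values will not be imputed", a reader might conclude that an event with a missing or partial onset date defaults to non-treatment-emergent. The documents do not establish this. SAP 3.4.4 imputes medication dates despite that sentence and leaves the details to a statistical programming plan that is not available here. Protocol 13.5 requires onset date and time. SAP silence on adverse-event dates is not a plan to exclude them.
- **A large bias.** A reader might suppose that several subjects are affected and multiply up. No document gives a count, and dividing by 20 would use the planned v3.0 enrolment when the safety tables run on all treated subjects.

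**Conclusion.** The gap is real and should be closed. As written, a recorded event that begins after consent and before the first study-drug dose, and worsens or becomes serious afterwards, is left out of the TEAE, serious TEAE, Grade 3 or higher and special-interest tables. The effect is undercounting only.

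The conclusion rests on two conditions: the event stays on a single record, and the rule is applied as stated, with no unstated exception. The effect is about 4.3 points per subject whose only qualifying event for a table is lost, on an assumed safety set of 23. The number of such subjects, and so the total effect, cannot be estimated from the documents. This is a correctable definition in a descriptive pilot. It does not affect the efficacy analysis.

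**What to change.** **SAP 3.6.1.** Keep the existing onset criterion and add a second one: *or with earlier onset, if it increases in severity or becomes serious on or after that dose.* Align the definition in Protocol 13.2.1.1.

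**Recording.** Choose one convention for worsening and state it in the protocol or the eCRF completion guidance. It can be a dated grade change on the same record, or a new record linked to the original. Do not run both without a rule to join them, because one event could then qualify twice. Under either convention, count the event once per subject in the tables.

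**Cost.** One added clause in the SAP, a matching line in the protocol, and one recording instruction. Treatment, visits and sample size do not change. The small downside is that TEAE counts rise slightly, and some added events will reflect surgery or induction more than study drug. The existing summaries by relationship to investigational product help readers judge those.
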